6.5 POOLING OF CENTRES

This section is not applicable because centre/country is not included in a statistical model.

6.6 HANDLING OF MISSING DATA AND OUTLIERS

6.6.1 Primary endpoint

Missing or incomplete AE dates will be imputed according to BI standards (see “Handling of missing and incomplete AE dates”) (6).

6.6.3 Other variables

6.6.3.2 Concomitant therapies

In case of (partially) missing start and end dates of concomitant therapies, the dates will be imputed so that the extent of exposure to the concomitant therapy is maximal, i.e. the first day (month) of the month (year) for incomplete start dates and the last day (month) of the month (year) for incomplete end dates. Imputed end dates must not be after date of death or last contact date as collected on the end of study eCRF page.

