4.2.2 Restrictions

4.2.2.1 Restrictions regarding concomitant treatment

Investigational therapy is not allowed during the entire study period of this open label extension trial.

There are no further restrictions for treatment of the underlying disease or other treatments for the ILD, thus allowing the underlying disease to be managed according to current standard practice (see cautionary notes below).

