6. GENERAL ANALYSIS DEFINITIONS

6.1 TREATMENTS

For treatment specifications, please refer to CTP Section 4.

The different periods of interest, as per CTP flow chart, are the following:

Note: the last day of each of the periods is excluded from the period. It defines the first day of the subsequent period.

- Post-IC period (optional^[a]): From date of informed consent to first nintedanib intake.
- Treatment period: From first nintedanib intake (or re-start of treatment if interruption) to last nintedanib intake (or day before start date of interruption if interruption) plus one day.
- Off-treatment (optional^[a]): From start date of interruption to re-start of treatment.
- Residual effect period^[b]: From last nintedanib intake plus one day to last nintedanib intake plus 28 days plus one day.
- Follow-up period (optional^[a]): From last nintedanib intake plus 28 days plus one day (after residual effect period) to last contact date (as collected on the end of study eCRF page) plus one day. This period is only created if last nintedanib intake took place more than 28 days before last contact date (as collected on the end of study eCRF page).
- Post-study period (optional^[a]): From last nintedanib intake plus 28 days plus one day or from last contact date (as collected on the end of study eCRF page) plus one day, whichever occurs later.

^[a] This period is optional insofar as it does not necessarily exist for all subjects.

^[b] In addition, a residual effect period of 7 days will be used for safety analyses to more closely reflect the period of time after the last nintedanib intake.

For subjects who did not receive any dose of nintedanib in extension trial, Post-IC period is the only period defined.

For subjects who died during the trial, periods with above defined start date after date of death do not exist and last existing period is defined until date of death plus one day only.

For safety analyses ([Section 7.8](#)), data from the treatment period, possible off-treatment periods and residual effect period will be considered as on-treatment.

6.2 **IMPORTANT PROTOCOL DEVIATIONS**

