7.2.2 Concomitant therapies

Concomitant therapies will be coded using the current World Health Organization Drug Dictionary (WHO-DD) version in use at BI at the time of (interim) database lock.

Concomitant therapies will be assigned to the following categories:

- Previous therapies: All therapies with a stop date before date of Visit 1 in extension trial.
- Baseline therapies: All therapies with a start date before date of first nintedanib intake in extension trial and a stop date after or on the day of Visit 1 in extension trial (or ongoing after completion of extension trial).
- On-treatment concomitant therapies: All therapies with a start date after or on the day of first nintedanib intake in extension trial and before or on the day of last nintedanib intake in extension trial.
- Post-study drug discontinuation therapies: All therapies with a start date after last nintedanib intake in extension trial and before or on the last contact as collected on the end of study eCRF page.

Concomitant therapies will be described over the entire duration of the extension trial. Similar summaries will be provided regarding the first 48 weeks or the first 96 weeks only, i.e. until Week 48/Week 96 time point (Day 379/Day 715, i.e. 378/714 days after date of Visit 1).

[Table 7.2.2: 1](#) and [Table 7.2.2: 2](#) summarise the concomitant therapy outputs which will be provided for analyses over the whole trial, over 48 weeks and over 96 weeks respectively, for each category of concomitant therapy created.

Summaries by Anatomical Therapeutic Chemical (ATC) classification and preferred name (PN) will use the ATC3 levels, and will be sorted by alphabetical ATC class and by decreasing order of overall prevalence (Total column) of PN within ATC class.

Summaries by Customised Drug Grouping (CDG) and PN will be sorted by alphabetical CDG name and by decreasing order of overall prevalence (Total column) of PN within CDG. CDGs are built using WHO-DD Standardised Drug Groupings (SDG), Sub-SDGs and ATC4 levels. CDGs are listed in [Section 9.2](#).

Table 7.2.2: 1 Concomitant therapy outputs over the whole trial

	By ATC and PN	By CDG and PN
Baseline therapies	X	X
On-treatment concomitant therapies	X	X
All baseline and on-treatment concomitant therapies	X	X
All baseline and on-treatment concomitant therapies with an incidence greater than 2% (in at least one treatment arm)	X	Not required
Post-study drug discontinuation therapies	Not required	Not required

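### Partial start dates in the month or year of Visit 1 turn concomitant therapies begun on nintedanib into baseline therapies

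*SAP*

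**What the plan says.** SAP 6.6.3.2 handles partly missing therapy dates by a maximal-exposure rule: "the dates will be imputed so that the extent of exposure to the concomitant therapy is maximal". For starts this means "the first day (month) of the month (year) for incomplete start dates". The section states one limit, and it concerns ends only: "Imputed end dates must not be after date of death or last contact date as collected on the end of study eCRF page". There is no corresponding floor for starts.

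SAP 7.2.2 sorts therapies by date. Baseline therapies are "All therapies with a start date before date of first nintedanib intake in extension trial", provided that they did not stop before Visit 1 (those still running when the trial ends are included). On-treatment therapies start between first and last intake, both days included. Later starts form a separate category after discontinuation of study drug. Tables 7.2.2: 1 and 7.2.2: 2 plan on-treatment outputs and a combined baseline plus on-treatment output, by ATC class and by customised drug grouping, over the whole trial and over 48 and 96 weeks.

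Protocol 6.2.1 has the first extension dose given in the clinic at Visit 1, so the dividing date is normally Visit 1 itself.

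**The concern.** Maximising exposure is a reasonable rule for how long a therapy lasted. SAP 7.2.2 also uses the imputed start for another purpose: whether the therapy was new after the first dose. For that question the rule is not neutral. Wherever the true start could lie on either side of Visit 1, it selects the earlier side.

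The records affected lie in the calendar month of Visit 1, or in its calendar year where only the year is known. This is when former placebo patients take nintedanib for the first time (Protocol 3.3), and Protocol 4.2.1.1 asks for early symptomatic treatment of diarrhoea. A medicine begun for such an event and recorded with the month only would be shown as something the patient brought into the trial. Among the therapy outputs in the available text, the on-treatment table is the one that isolates new starts, so that is where the error would show. The columns by parent-trial arm might be affected unequally.

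**Working it through.** The plan gives no figure on this point, so there is none to reproduce. The check applies the two SAP sections as date rules.

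**Inputs**
- Imputed start: 1st of the month if the day is missing, 1 January if day and month are missing (SAP 6.6.3.2).
- Baseline: start before first intake and stop on or after Visit 1. On-treatment: first intake ≤ start ≤ last intake (SAP 7.2.2).
- First intake = Visit 1 (Protocol 6.2.1).
- Assumed: Visit 1 equally likely on each of 365 days (calendar of 2019).

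**Examples**

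| Visit 1 | True start | Recorded as | Imputed | Class |
|---|---|---|---|---|
| 12 Jun 2019 | 20 Jun 2019 | Jun 2019 | 1 Jun 2019 | baseline (wrong) |
| 12 Jun 2019 | 20 Nov 2019 | 2019 | 1 Jan 2019 | baseline (wrong) |
| 12 Jun 2019 | 20 Jul 2019 | Jul 2019 | 1 Jul 2019 | on-treatment (right) |
| 12 Jun 2019 | 2 Mar 2020 | 2020 | 1 Jan 2020 | on-treatment (right) |
| 1 Jul 2019 | 20 Jul 2019 | Jul 2019 | 1 Jul 2019 | on-treatment (right) |

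The error is confined to the month of Visit 1 (day missing) or its year (month and day missing).

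**Therapies truly begun on or after first intake**
- Day missing, same month: baseline for 365 − 12 = 353 Visit 1 dates. The 12 exceptions are the firsts of the months. Over all pairs of Visit 1 date and later start in that month, 5,373 / 5,738 = 93.6% are classed as baseline.
- Only the year known, same year: baseline for 364 of 365 dates (exception: 1 January). Over all pairs, 66,430 / 66,795 = 99.5%.

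**All day-missing starts in the Visit 1 month.** Take Visit 1 day and start day as independent and uniform on 1–30 (900 pairs), with the therapy still in use at Visit 1:
- begun on or after Visit 1: (30 × 31 / 2) / 900 = 465 / 900 = 0.517
- classed as baseline: 29 / 30 = 0.967
- begun on or after Visit 1 but classed as baseline: (465 − 30) / 900 = 435 / 900 = 0.483

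If starts on or after Visit 1 are *k* times as dense as before it, the last share is 435*k* / (465*k* + 435): 870 / 1,365 = 0.637 for *k* = 2 and 1,305 / 1,830 = 0.713 for *k* = 3. A therapy that ended before Visit 1 is a previous therapy and does not enter.

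**Effect on the table.** The share of start dates with a missing day is not documented. If it were 2% to 10% of starts in the Visit 1 month, misclassified records would be 0.483 × 0.02 = 1.0% to 0.483 × 0.10 = 4.8% of that month's starts. As a share of those truly begun on or after Visit 1, the loss would be (435 / 465) × 2% = 1.9% to (435 / 465) × 10% = 9.4%. The 2–10% is an assumption.

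**The other end of treatment.** For starts 1 to 28 days after last intake, with last intake equally likely on each of 365 days (calendar of 2021), the rule moves about 52% of day-missing starts and about 96% of year-only starts back to on or before last intake. These then count as on-treatment, an error in the opposite direction.

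**The case against.** The strongest case on the other side is that the effect is small and conceals nothing. Therapies moved to baseline remain in the combined table for the whole trial, 48 weeks and 96 weeks. Concomitant therapy is reviewed at weeks 2, 4, 8 and 12 (Protocol flowchart) and its start date is a named source-data item (Protocol 8.3.1), so partial dates for early new therapies may be uncommon. SAP 7.2 is descriptive only. AE records also carry a therapy-required attribute (SAP 7.8.1), and sections absent from the public text could hold further outputs. All of this stands as a limit on size. It does not change how the date rule sorts an ambiguous start.

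Three stronger readings are tempting, and the documents do not support them.

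- *That the plan systematically undercounts treatment started on nintedanib.* The rule undercounts around Visit 1 and can overcount after the last dose, so the net direction is not fixed.
- *That therapies started in the 28 days after the last dose are wrongly left untabulated.* SAP 6.1 does say that "data from the treatment period, possible off-treatment periods and residual effect period will be considered as on-treatment", but only for the safety analyses of Section 7.8. Concomitant therapies belong to Section 7.2, which has its own category, "All therapies with a start date after last nintedanib intake in extension trial and before or on the last contact" date on the end-of-study page, and both output tables explicitly mark it as not required. A therapy begun after the last capsule is not newly started on nintedanib. Such a table would also be unevenly filled, because Protocol 6.2.3 requires a follow-up visit only after stopping for an adverse event.
- *That ILD therapies barred in INBUILD become available at Visit 1 and surge there.* Protocol 4.2.2.1 says of the extension that "There are no further restrictions for treatment of the underlying disease or other treatments for the ILD", but Protocol 10.1 lists only the parent trial's entry exclusions. Restrictions during INBUILD are not described.

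**Conclusion.** The point holds as a minor defect in the classification rule. A therapy begun after first intake, with a partial start date in the month or year of Visit 1, is classed as baseline unless Visit 1 fell on the 1st of the month or, for year-only dates, on 1 January. It is then missing from the on-treatment tables.

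The 353 of 365 and 364 of 365 follow from the rules and first intake at Visit 1. The 48% rests on uniform dates and rises to 64–71% if starts are two to three times as dense after Visit 1. The absolute effect cannot be stated without the share of partial dates. The primary endpoint, AE incidence (SAP 7.8.1.4), does not use these rules.

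**What to change.** Add one sentence to SAP 6.6.3.2, for the baseline/on-treatment split only: where a partial start date is compatible with a start on or after first intake, the therapy is baseline only if it was already recorded at Visit 1 or as ongoing in INBUILD at EOT_B; otherwise its start is set to the date of first intake, or it is shown in a separate start-undetermined row. Choose one of the two alternatives before programming. Keep the maximal-exposure rule for duration.

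The cost is the SAP wording and a look-up. The flowchart collects concomitant therapy at Visit 1, and Protocol 7.1 allows parent-trial data to be taken into account. The documents do not say whether the database keeps the visit at which a therapy was entered, or whether INBUILD therapy records will be transferred (flowchart footnote 3 names only demographics and medical history). Confirm this first; if neither source is usable, the undetermined row suffices.

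The downside is that a few therapies begun just before Visit 1 but not recorded then may move to on-treatment. No additional table for the period after the last dose is needed.

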6.6.3.3 Exposure

6.6.3.3.1 Permanent trial drug discontinuation

A missing or incomplete date of last nintedanib intake will be imputed that the derived date is the latest possible date which is on or before date of death, and on or before last contact date from end of study eCRF page.

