³ Demographics will be collected from the INBUILD® database. Medical History will be collected from the INBUILD® database and may be updated with relevant new information.

⁴ Medical conditions that are occurring concomitantly at visit 1 will be recorded as baseline conditions in the eCRF, including any ongoing AEs from INBUILD® at the time of Visit 1.

⁵ Intermediate lab tests ('a'-Visits) to be done as needed for additional safety monitoring (see sections [4.2.1.2](#) and [5.2.3](#)) at the discretion of the investigator. 'a' visits do not necessarily need to be a site visit.

⁶ Urine pregnancy tests should be performed in all women of childbearing potential every 4-6 weeks: at least at every visit and if necessary, additionally at home or at a local doctor / laboratory. If urine pregnancy test is not acceptable to local authorities, a blood test can be done at a local laboratory. Women of childbearing potential will be instructed accordingly.

⁷ Visit X stands for Visit 9, Visit 10 etc. Visits should be repeated every 12 weeks until at least visit 12 (Week 96). Thereafter, visits will be repeated every 12 weeks until the patient's end of trial (see section [3.3.4](#)).

⁸ End of Treatment (EOT) Visit to be performed for all patients, as soon as possible after last drug intake in this extension trial (refer to section 3.3.4 and 6.2.2).

⁹ A follow-up (FU) visit should be planned for 28 days (+ 7 days window) after last drug intake in case trial medication had to be discontinued permanently due to adverse events. This visit may be conducted by telephone.

¹⁰ After the individual patient's end of the trial the investigator should report only any occurrence of cancer, related SAEs and related AESIs of which the investigator may become aware of and only via the SAE form, please see section [5.2.5.2.1](#).

TABLE OF CONTENTS

CLINICAL TRIAL PROTOCOL.....	1
CLINICAL TRIAL PROTOCOL SYNOPSIS	2
FLOWCHART	4
TABLE OF CONTENTS	6
ABBREVIATIONS	9
1. INTRODUCTION.....	12
1.1 MEDICAL BACKGROUND	12
1.2 DRUG PROFILE	13
1.3 RATIONALE FOR PERFORMING THE TRIAL	17
1.4 BENEFIT - RISK ASSESSMENT.....	17
2. TRIAL OBJECTIVES AND ENDPOINTS.....	19
2.1 MAIN OBJECTIVES, PRIMARY AND SECONDARY ENDPOINTS.....	19
2.1.1 Main objectives.....	19
2.1.2 Primary endpoint(s).....	19
2.1.3 Secondary endpoint(s)	19
3. DESCRIPTION OF DESIGN AND TRIAL POPULATION.....	20
3.1 OVERALL TRIAL DESIGN AND PLAN	20
3.2 DISCUSSION OF TRIAL DESIGN, INCLUDING THE CHOICE OF CONTROL GROUP(S)	20

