4.1.4 Drug assignment and administration of doses for each patient

The treatment for an individual patient will be assigned by means of an IRT contact during Visits 1, 3, 5, 6, 7, 8 to X. Each patient will receive active drug at a dosage of 150mg bid or 100mg bid.

Trial medication will consist of 1 capsule twice daily throughout the trial. Wallets covering 30 days + 5 days reserve treatment will be dispensed to the patient:

- 1 wallet at Day 1 (Visit 1) (30 days plus 5 days reserve)
- 2 wallets at Visit 3 (60 days plus 10 days reserve)
- 3 wallets at Visit 5, Visit 6, Visit 7, Visit 8 and Visit X (90 days plus 15 days reserve)

Nintedanib will be administered orally on a twice daily basis (bid). The patients should swallow the trial medication unchewed together with a glass of water (~250mL), and should observe a dose interval of 12 hours. Nintedanib needs to be taken at the same times every day (between 06:00 and 11:00 in the morning, and between 18:00 and 23:00 in the evening). Because nintedanib may cause stomach discomfort, it is recommended to take the trial medication with food.

A forgotten dose should be skipped if the time window to the next dose is less than 8 hours. The next dose should be taken as scheduled.

Nintedanib should only be dispensed to participating patients according to the protocol by authorised personnel as documented in the form “Trial Staff List”.

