6.2.2 Treatment period(s)

Subsequent clinic visits will be scheduled after 2, 4, 8, 12, 24, 36 and 48 weeks of treatment (Visits 2- 8). After the first 48 weeks of treatment (Visit 8), complete clinic visits will be scheduled every 12 weeks until at least Week 96 (Visit 12) and thereafter until the patient's end of trial.

Intermediate lab tests ('a' visits) will be performed if needed at 18, 30 and 42 weeks (Visits 5a, 6a and 7a) at the discretion of the investigator. The laboratory samples taken at these visits and any samples taken for additional safety monitoring (see sections [4.2.1.2](#) and [5.2.3](#)) may be collected at the office of a local doctor using trial specific lab kits that will be sent to a central laboratory for analyses. These kits will be provided to patients at study visits as applicable.

If possible, ECG should be performed prior to blood draw.

For detailed description of the trial procedures at each visit and dispensing schedule, please refer to [section 5](#) and the [Flowchart](#).

Dose Modification Visit

If the dose is reduced or increased (refer to section [4.1.3](#)) patients may need to come to the investigational site for a dose modification visit where the following will be performed:

- Physical examination including weight
- Vital signs

- Assessment of adverse events and concomitant therapy since last visit
- Assignment of new dose in IRT and trial medication dispensation
- Trial medication will be collected and drug accountability and treatment compliance will be reviewed

End of Treatment (EOT)

If a reason for drug discontinuation is met or when the trial is terminated due to one of the reasons mentioned in section [3.3.4](#), an End of Treatment Visit (EOT) should be scheduled as soon as possible after last drug intake for all patients. Reason for discontinuation must be documented in the eCRF. IRT should always be notified on end of treatment (EOT).

Adverse events that are ongoing at EOT should be followed up according to section [5.2.5.2.3](#).

For detailed description of the trial procedures at the EOT visit, please refer to the [Flowchart](#).

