6.2.3 Follow up period and trial completion

A follow-up (FU) visit must be conducted 28 days after last drug intake if trial medication was discontinued permanently due to adverse events. A FU visit does not need to be conducted for patients who stop for any other reason.

For detailed description of the trial procedures at the FU visit, please refer to the Flowchart.

If the reason for removal of a patient from the treatment is an adverse event, the patient must be followed until complete resolution or stabilization of the event for at least 28 days after the onset of the event or until follow-up is considered adequate by the investigator and clinical monitor.

A patient will be lost to follow-up if the investigator is not able to contact him/her despite multiple attempts. Every effort must be made; at least 2 telephone contacts plus 1 mailing should be documented. The site must notify the clinical monitor prior to designating a patient as lost to follow up.

For patients who permanently discontinue nintedanib due to adverse events, the FU Visit will be the trial completion visit. For all other patients the EOT visit will be the trial completion visit.

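### The rule for a missing last-intake date is not capped at the EOT visit, so for a patient who stopped for an AE and had the FU visit it can place the stop about 28 to 35 days too late

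*SAP*

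**What the plan says.** SAP 6.6.3.3.1 covers both kinds of gap: "A missing or incomplete date of last nintedanib intake will be imputed" so that "the derived date is the latest possible date which is on or before date of death, and on or before last contact date", the latter taken from the end-of-study eCRF page. No other bound is listed, and the reason for stopping plays no part.

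The protocol ties two later visits to the last intake:

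- **EOT visit.** Section 6.2.2 says it "should be scheduled as soon as possible after last drug intake for all patients". Flowchart footnote 8 says the same.
- **FU visit.** Section 6.2.3: "A follow-up (FU) visit must be conducted 28 days after last drug intake if trial medication was discontinued permanently due to adverse events". Flowchart footnote 9 gives the window: "A follow-up (FU) visit should be planned for 28 days (+ 7 days window) after last drug intake". There is no allowance on the early side, and the contact may be by telephone.

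Section 6.2.3 also says which visit ends participation: "For patients who permanently discontinue nintedanib due to adverse events, the FU Visit will be the trial completion visit", and "For all other patients the EOT visit will be the trial completion visit".

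**The concern.** The rule looks for the latest date the patient could still have been taking drug, but its upper limit for AE stops is a contact that the protocol sets at least 28 days after the last dose. An imputed date equal to the FU date therefore conflicts with the protocol's own definition of that visit. It also falls after EOT, when drug is collected and medication is recorded as terminated.

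The date of last intake feeds exposure duration and total dose (SAP 5.4.3.1) and the boundaries of the treatment and residual-effect periods (SAP 6.1). The patients concerned stopped because of an AE, a group that matters in a trial whose objective is long-term tolerability and safety. Patients who stop for other reasons complete at EOT, soon after the last intake, so the rule does them little harm.

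**Working it through.** The plan gives no figure of its own to reproduce. The check is day arithmetic with the true last intake at day 0.

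**Inputs**
- Bounds of the rule: death and last contact (SAP 6.6.3.3.1).
- FU visit: day +28 to +35 (protocol 6.2.3 and flowchart footnote 9).
- Last contact taken as the FU date. This is inferred from FU being the completion visit for AE stops.
- Exposure = last intake − first intake + 0.5 days; months = days / 30.5; daily dose 0.3 g at 150 mg bid and 0.2 g at 100 mg bid (SAP 5.4.3.1).
- Residual-effect period: 28 days, with an additional analysis using 7 days (SAP 6.1).
- End of AE time at risk: the earliest of last intake + 28 days, last contact, death and database lock (SAP 7.8.1.1).

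**1. Fully missing date, AE stop, FU held.** Imputed date = last contact = FU date = day +28 to +35. The error is 28 to 35 days, or 28/30.5 = 0.92 to 35/30.5 = 1.15 months.

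**2. Exposure duration.** Relative overstatement = error / true exposure:

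| True exposure (days) | Error 28 days | Error 35 days |
|---|---|---|
| 91 | 30.8% | 38.5% |
| 365 | 7.7% | 9.6% |
| 673 (planned Week 96 day) | 4.2% | 5.2% |

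**3. Total dose.** At 150 mg bid: 28 × 0.3 = 8.4 g to 35 × 0.3 = 10.5 g. At 100 mg bid: 28 × 0.2 = 5.6 g to 35 × 0.2 = 7.0 g. These are upper limits, reached if all the added days are counted as dosed.

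**4. Period assignment.** With the 7-day residual-effect period, on-treatment should end at day 7. Under the imputed date the treatment period itself runs to day 28 or later, so AEs from days 8 to 28 are counted as on-treatment (to day 35 if FU was at the end of its window). With the 28-day period, the nominal end moves from day 28 to day 28 + 28 = 56 up to 35 + 28 = 63, which is past last contact. In practice only events in days 29 to 35 could be added.

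**5. AE time at risk (primary endpoint rate).** The true end is min(28, FU) = day 28. The imputed end is min(FU + 28, FU) = FU = day 28 to 35. The error is 0 to 7 days per affected patient.

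**6. Whole-trial compliance.** SAP 5.4.2.1 does not calculate compliance without a final assessment on or after the day of last intake. The flowchart schedules compliance at EOT and not at FU. With last intake imputed to the FU date, the EOT count comes before it, so compliance may be set to missing.

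**7. Month known.** Imputed date = the earlier of month end and FU. Over every calendar day of 2020 and 2021, with FU at +28 to +35, the error is 0 to 30 days (mean about 15). The imputed date falls less than 28 days before FU, which the protocol's timing excludes, in about 85% of cases: 97% if FU is at +28 and 74% if it is at +35.

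**The case against.** The strongest objection is rarity. Both EOT and FU are timed from the last intake, so a site that held FU on schedule must have known that date. EOT also involves drug collection, accountability and an IRT notification. Dates are more likely to be missing in patients who died or were lost without an FU visit, where the 28-to-35-day mechanism does not operate. This stands as a limit on frequency. It does not make the rule right when it is used.

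Two further defences are weaker. SAP 6.6.3.2 takes the same maximal-exposure approach for concomitant therapies, so this could be called a house convention; but here the protocol supplies a tighter limit from a planned visit. One could also argue that the latest possible date already implies EOT, but the sentence lists its bounds and EOT is not among them.

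A reader might infer more than the documents support:

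- **That compliance is inflated** by 28 × 2 = 56 to 35 × 2 = 70 expected capsules. SAP 5.4.2.1 points to a missing value instead.
- **That the error always lengthens exposure, including in lost patients.** Protocol 6.2.3 defines a lost patient as one who cannot be contacted. Last contact then normally precedes the loss, and dosing may have continued after it.
- **That time to premature discontinuation is shifted by the same amount.** SAP 6.6.3.3.2 refers to a separate imputation rule for time-to-event analyses in Section 6.6.2.2. Neither that section nor the censoring table for this analysis is in the public text.
- **That the primary result is at risk.** The cap at last contact in SAP 7.8.1.1 prevents this.

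**Conclusion.** The point holds in a narrow form. For an AE stop with FU held on schedule and a fully missing last-intake date, the stated rule gives a stop date about 28 to 35 days too late and after EOT. This overstates exposure duration and total dose, misassigns events in the additional 7-day residual-effect analysis, and may remove the patient from the whole-trial compliance summary. With the month known, the shift is at most 30 days and the result is not always impossible.

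This assumes that the end-of-study last contact date equals the FU date (a later contact would make the error larger) and that the patient did not die, withdraw or become lost before FU. The documents do not say how many dates will be missing, so no count of affected patients can be given. The overall effect is probably small. This is a minor correction, worth making because it costs almost nothing.

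**What to change.** Add a third bound to SAP 6.6.3.3.1: the imputed date must also be on or before the EOT visit date, where an EOT visit was held. The remaining error is then the gap between last intake and EOT, which the protocol wants short but does not fix in days.

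Where EOT is missing but an FU visit was held on schedule, use FU date minus 28 days as a backup bound. With FU in its window this leaves an error of 0 to 7 days. It relies on FU having been on time, which is hard to confirm when the last-intake date is missing; an FU held early would make the bound too early. It should therefore remain a backup.

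A bound from dispensed supply is tempting, since the protocol dispenses "3 wallets at Visit 5, Visit 6, Visit 7, Visit 8 and Visit X (90 days plus 15 days reserve") at a time, or 3 × 70 / 2 = 105 days. It is not advised: protocol 4.2.1 allows repeated interruptions of up to 4 or 12 weeks, so supply can validly last longer and the bound could cut off real exposure.

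The cost is one sentence in the SAP and minor programming with visit dates already collected. The downside is slightly shorter stated exposure for the few affected patients.
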